Xpert MTB/RIF for stools has also been considered in several studies (21-26) but its use is not yet recommended by the WHO. The sensitivity of the stool Xpert ranged between 45 and 83%, which suggests that it is a potential alternative screening test for children with suspected TB when sputum is unavailable. In one of the studies (21), stool Xpert could rapidly confirm TB in children who present with radiologic findings suggestive of severe TB.

The main challenge is confirming TB diagnosis with the gold standard – TB culture. Thus, many of the studies had very few patients (all of them < 75 children). However, the evidence suggests that stools, which are easily obtainable, are an appropriate alternative sample for the diagnosis of pulmonary TB, especially for children unable to give respiratory samples. This is true for both HIV positive and negative individuals. “Valid specimens” for the detection of DNA of *M. tuberculosis* with Xpert include respiratory specimens from sputum sampled by expectoration, sputum induction, gastric aspirates, or nasopharyngeal aspirates and can include the use of a stool sample (19,20).

Urine Xpert has produced less interest among clinicians. Of the few studies (27,28,29), all of them focus on adult HIV+ patients. As main conclusions, urine-based MTB/RIF, alone or in combination with LAM antigen detection and/or sputum Xpert MTB/RIF, may potentially aid the

diagnosis of TB in HIV-infected patients with advanced immunosuppression when sputum-based diagnosis is not possible. Further studies are necessary to assess the utility of urine Xpert MTB/RIF in the diagnosis of TB in children.

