- Persistent fever ($>38^{\circ}\text{C}$) beyond one week after exclusion from classical causes such as malaria or pneumonia
- Persistence or aggravation of fatigue
- Chest radiographs imaging suggestive of tuberculosis

4. Case with diagnosis of tuberculosis (40,41)

- **Confirmed TB:** patients with Xpert MTB/RIF Ultra positive (or TB culture positive when available) in a respiratory sample (pulmonary TB) or in other sample, such as CSF, lymph node or other tissue/liquid (extra pulmonary TB); TB LAM positive in HIV-infected patients.
- **Unconfirmed TB:** no microbiological confirmation but clinical diagnosis of TB and started on anti TB treatment (as established in Appendix 5).
- **Unlikely TB:** good response to other treatments (antibiotic, nutritional support, etc.) and no suggestive symptoms after 1 week of admission and until the 2 month follow-up.

8. Study procedures

a. Identification of participants

Eligible children will be identified upon admission to paediatric ward, ITFC, PICU/NICU (in Bissau) or as suggestive cases in OPD. The identification of suspected TB cases will be mainly based on clinical criteria. A diagnostic algorithm (Appendix 4) will be applied to all suspected cases. The populations of interest for this study are hospitalized children, severely malnourished (SAM) and HIV positive or exposed children.

b. Laboratory

1. Sample collection

All patients included in the study will have requested one stool and one urine sample. The team will follow a specific SOP for respiratory sample collection (naso-pharyngeal aspirate, gastric lavage or spontaneous sputum), stools, urine and lymph nodes (or other validated extra pulmonary samples) as described in the appendixes. In hospitalized children, all samples will be collected during hospitalisation and patients not capable of producing the required sample (stools/urine) during this period will be excluded from the study. For ambulatory patients, samples will be collected within 2 hours and, if child not capable of producing stools/urine, samples will be requested to be brought by parents or guardians the day after.

2. Laboratory procedures

Xpert MTB/RIF Ultra will be performed to respiratory or extra pulmonary validated samples, stools and urine for all patients at baseline, and for those with negative results and persistent symptoms, will be repeated after 1 to 2 weeks.

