TB LAM in urine will be tested in all Malakal patients (starting from November 2021) and the result (negative/positive and grade 1-4) recorded in the CRF Lab form. The result will be shared with Research Manager who will only communicate to clinicians in case of HIV-infected patient; in these patients, TB LAM will be used as per clinical protocol.

3. Sample handling and storage

Respiratory specimens will be collected at the clinic and samples will be kept between 2 and 8°C until processed. Processing will be done within the 24 hours and not more than 72 hours after collection. A sterile stool container and instructions will be provided to the parent or guardian for specimen collection and handling. Following delivery to the laboratory, the stool specimen will be kept in a cool dry place and processed within 2 hours. Samples obtained in this study will adhere to all local laboratory procedures governing the storage of biological specimens.

c. Linkage to care for HIV/TB patients

All patients HIV positive will be enrolled into **HIV care** either in MSF program (Malakal) or MoH programs (Bissau). MSF will guarantee that all children will be started on ART after 2 weeks of TB treatment (or as soon as possible if TB has been excluded) or differed to 4-6 weeks in case of TB meningitis.

All TB cases (confirmed or unconfirmed) will be enrolled in **TB care** in MSF program (Malakal) or MoH program (Bissau). MSF will ensure all patients to be started on adequate weight-based dose fix combinations and followed up during the length of treatment. All children diagnosed of DRTB will be initiated on DRTB treatment regimen according to national recommendation.

In patients where stool samples yield positive results and sputum tests are negative, stool results will be communicated to Study Coordinator on site for interpretation and appropriate clinical management. Where stools results are concordant with sputum results, no additional information will be provided.

As a transversal study, it is not foreseen to follow-up patients for study purposes. The follow-up will be required though for the study “Evaluating POCUS to improve TB diagnosis in children”.

d. Data collection

The following information will be noted in an individual case study report form (CRF) for each participant:

1. DEMOGRAPHIC INFORMATION AND INFORMED CONSENT OF PATIENTS:

- Study code
- Date of birth / age
- Sex
- Parent or guardian's informed consent: Yes / No

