- Consent to be traced in case of defaulting

2. CLINICAL AND DIAGNOSTIC INFORMATION OF STUDY PARTICIPANTS AT BASELINE:

[figure not shown]
- Entry point (OPD, TB or HIV or Nutrition program, IPD)
- History of TB contact, HIV or malnutrition
- Temperature (axillary) (°C)
- Weight and size
- Nutritional status
- Co-morbidities: malaria, respiratory infection, HIV status
- Signs and clinical symptoms suggestive of tuberculosis
- Final diagnosis
- TB treatment started: Yes / No
- Date of TB treatment started

[figure not shown]
3. LAB EXAMS INFORMATION:

- Program identification number
- Inclusion number in the study
- Date of respiratory sample collection
- Type of procedure: spontaneous sputum, naso-pharyngeal aspirate, gastric aspiration
- Date of Xpert MTB/RIF Ultra in respiratory sample performed (1 sample)
- Result of Xpert MTB/RIF Ultra (negative, positive RIF resistance negative, positive RIF resistance positive, indeterminate)
- Date of stools collection
- Date of Xpert MTB/RIF Ultra in stools performed (1 or 2 samples)
- Result of Xpert MTB/RIF Ultra (negative, positive RIF resistance negative, positive RIF resistance positive, indeterminate)
- Date of urine collection
- Date of Xpert MTB/RIF Ultra in urine performed (1 or 2 samples)
- Result of Xpert MTB/RIF Ultra (negative, positive RIF resistance negative, positive RIF resistance positive, indeterminate)

e. Flow of patients

OPD patients who don't need hospitalization will be requested to stay in observation for 2 hours to perform all exams after obtaining the informed consent. If the participant is not able to produce stools within this time, s/he will be requested to bring the sample once produced at home (all information in Appendix 3). Please, find the flow in the following page.

9. Safety Considerations

There are safety considerations related to infection control of TB, even if children are only considered contagious after they acquire the capacity of expectorating (> 8 years old). For older children, isolation procedures for coughing patients, as well as protection measures for medical staff, need to be implemented. Lab staff needs to wear respirator and gloves when manipulating samples for Xpert MTB/RIF Ultra. Safety procedures related to Xpert MTB/RIF Ultra need to be in place.

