Angular deformation of the spine (gibbous)	
--	--------------------------

Lymphadenopathy	
Subacute meningitis	
Abdomen distended with ascites	
> 2 weeks of diarrhoea	
Painless enlarged joints	
Pleural effusion	
Other	 Specify: _____
POCUS done:	Yes  No 
	Date: / /

Information at discharge: final diagnosis **Date:** / /

Confirmed pulmonary TB	
Suspected pulmonary TB	
Confirmed extra pulmonary TB	
Suspected extra pulmonary TB	
Unlikely TB	
Other	 Specify: _____

TB treatment

Started: Yes No Date ATT started: / /
 Regimen: _____

Follow-up after 2 months of discharge (POCUS participants) **Date:** / /

Nutritional status:	Not significantly malnourished 	MAM 	SAM 
TB treatment prescribed:	Yes 	No 	
Under TB treatment:	Yes 	No 	
If interruption, specify reason:			
Smear at month 2:	Done 	Positive 	Negative 
Not done 			
POCUS done:	Yes  No 	Date: / /	

[figure not shown]
TB patients: follow-up after 6 months of discharge (POCUS participants) **Date:**
 / /

Nutritional status:	Not significantly malnourished 	MAM 	SAM 
TB treatment finalised:	Yes 	No 	
Smear at month 6:	Done 	Positive 	Negative 
Not done 			
POCUS done:	Yes  No 	Date: / /	

TB treatment outcomes:

Cured:		Defaulted:		Date: /
/				
Completed:		Death:		
Failure:		Not evaluated:		

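### If secondary objective 1 is analysed as accuracy against confirmed plus unconfirmed TB, a child treated partly because of a positive stool Ultra can count as TB in the reference, and nothing readable prevents or bounds this

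*Combined protocol and SAP*

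**What the plan says.** All references are to the combined protocol and SAP.

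- **Objective.** Section 6.b, objective 1, asks for the sensitivity and specificity of Ultra for rifampicin resistance in stool and urine, taking confirmed and unconfirmed TB cases as a composite. Section 10 does not say how this will be analysed. Its one stated accuracy outcome is stool and urine against the gold standard.
- **Reference label.** In section 7.e.4, unconfirmed TB means "no microbiological confirmation but clinical diagnosis of TB and started on anti TB treatment (as established in Appendix 5"). The Appendix 5 work-up lists Xpert in stool and urine among the bacteriological tests.
- **Release of results.** Section 8.c covers children whose stool is positive and sputum negative: "stool results will be communicated to Study Coordinator on site for interpretation and appropriate clinical management". It gives no rule for urine.
- **Timing.** Section 8.b.1: "In hospitalized children, all samples will be collected during hospitalisation". The clinical CRF in Appendix 4 has a block headed "Information at discharge: final diagnosis".
- **Masking.** None is described for the diagnosis with respect to stool or urine Ultra. For TB LAM, section 8.b.2 does limit disclosure: the result goes to the Research Manager, "who will only communicate to clinicians in case of HIV-infected patient".
- **Recorded data.** Section 8.d includes "Date of TB treatment started", and Appendix 4 adds treatment yes/no and regimen. Appendix 17 records every stool and urine result with its dates. No field records why treatment was started.

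**The concern.** The plan's main comparison uses Ultra in sputum or a validated extrapulmonary sample. The composite is the only stated look beyond that reference, so it is where children positive in stool or urine but negative on the reference would be judged. If some of them are labelled TB because of the stool result, the index test has helped to write its own reference. The composite then cannot show whether those positives were true or false.

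Section 8.c concentrates the release of stool results in exactly this discordant group. For inpatients the final diagnosis can be set with the index results already known. Follow-up is not foreseen for this study (it belongs to the companion ultrasound study), so no step here would later correct the label.

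**Working it through.** **The plan's own figures (section 7.d.4).** With sensitivity 60%, precision 12% and an assumed 95% level: 1.96² x 0.60 x 0.40 / 0.12² = 64.02, matching the stated 64. Then 64 / 0.20 = 320, and 320 / 0.98 = 326.5, rounded up to 327. Both match.

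**Children at issue.** Reference-negative: 320 - 64 = 256. With specificity 95%, stool-positive and reference-negative: 256 x 0.05 = 12.8. Reference-positive and stool-positive: 64 x 0.60 = 38.4.

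**Inputs not in the plan (assumed).**
- U: reference-negative children who would be diagnosed and treated on clinical grounds anyway.
- p: stool positivity among those U children, 5% or more.
- f: share of the remaining stool-positive children who are treated because of the stool result.
- Every child outside the composite is counted as not having TB.

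**Formulas.** a = U x p; r = 12.8 - a; k = f x r.
- Specificity = 1 - (r - k) / (256 - U - k)
- Sensitivity = (38.4 + a + k) / (64 + U + k)

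**Results as f goes from 0 to 1.**

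| U | p | r | Specificity | Sensitivity |
|---|---|---|---|---|
| 0 | n/a | 12.8 | 95.0 to 100% | 38.4/64 = 60.0% to 51.2/76.8 = 66.7% |
| 64 | 5% | 9.6 | 95.0 to 100% | 41.6/128 = 32.5% to 51.2/137.6 = 37.2% |
| 64 | 10% | 6.4 | 96.7 to 100% | 44.8/128 = 35.0% to 51.2/134.4 = 38.1% |
| 64 | 15% | 3.2 | 98.3 to 100% | 48/128 = 37.5% to 51.2/131.2 = 39.0% |
| 64 | 20% | 0 | 100%, no shift | 51.2/128 = 40.0%, no shift |

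The largest sensitivity shift found is near U = 7, p = 5%: 38.75/71 = 54.6% to 51.2/83.45 = 61.4%, or 6.8 points.

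**Scale.** At U = 64, p = 5%, f = 0, the 95% half-widths are 1.96 x √(0.95 x 0.05/192) = 3.1 points for specificity and 1.96 x √(0.325 x 0.675/128) = 8.1 points for sensitivity. The sensitivity shift there (at most 4.7) stays inside sampling error. The specificity shift can exceed it only when p is low and f is high.

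**Two-way count from recorded data (U = 64, p = 5%, f = 0.5).** Treated, stool-positive and reference-negative: 3.2 + 4.8 = 8 children.
- Counted as TB: specificity 1 - 4.8/187.2 = 97.4%; sensitivity 46.4/132.8 = 34.9%.
- Counted as not TB: specificity 1 - 12.8/195.2 = 93.4%; sensitivity 38.4/124.8 = 30.8%.
- The values with no index-driven treatment (95.0% and 32.5%) lie inside both ranges.
- Excluded: specificity 1 - 4.8/187.2 = 97.4%, no lower than counting them as TB. At f = 1 exclusion gives 182.4/182.4 = 100%.

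**Rifampicin reading.** Appendix 12 gives a rifampicin result only where MTB is detected. Unconfirmed children therefore have no independent rifampicin reference call, and the composite cannot serve as a reference for them.

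**The case against.** The strongest reply is that objective 1 is worded for rifampicin resistance, so a composite TB-detection analysis is an inference. That stands, and the point is conditional for that reason. The rifampicin reading does not rescue the composite, however, so section 10 needs a statement either way.

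It can also be said that a rule may sit in the Appendix 5 flowchart, the patient-flow figure or Appendix 18, none of which can be read here. That stands too: the claim covers the readable text only.

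A reader might infer more than the documents support:

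- **That such a child automatically becomes TB.** Section 8.c sends the result for interpretation, and 7.e.4 requires a clinical diagnosis as well as treatment. Entry is possible, not certain.
- **That urine follows the same route.** Section 8.c releases stool only. Urine Xpert is listed in the Appendix 5 work-up, but no release rule is given.
- **That a stool result could make a child confirmed.** Section 7.e.4 allows a positive result "or in other sample, such as CSF, lymph node or other tissue/liquid", and the background on Xpert says valid specimens "can include the use of a stool sample". This is weak. Sections 7.d.4 and 8.b.2 and the CRF Lab keep stool and urine apart from validated extrapulmonary samples, and the second phrase describes the literature.
- **That the data cannot identify these children.** Results and dates in Appendix 17, crossed with diagnosis and treatment date in Appendix 4, identify every treated, index-positive, reference-negative child. What is missing is only whether the result drove the decision.

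**Conclusion.** The point holds as a cheap improvement to a secondary result. If objective 1 is analysed against confirmed plus unconfirmed TB, the readable text allows incorporation of the stool result into the reference and plans nothing to bound it. About 13 children are exposed on the plan's assumptions. The shift is 0 to 5 points of specificity and 0 to about 7 points of sensitivity. The top of each range requires every otherwise undiagnosed stool-positive child to be treated because of the result, and U, p and f are all assumed. The specificity figures also treat everyone outside the composite as TB-free, which is simpler than the plan's definition of unlikely TB.

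Two further inferences should be resisted. The primary comparison in 6.a is not affected, because its reference is Ultra in sputum or a validated extrapulmonary sample. Nor can the composite be called biased upwards relative to the truth: some of these children may truly have TB, so the direction of error is unknown.

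**What to change.** Keep releasing stool results for care. Then:

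1. In section 10, state which comparison objective 1 means, and that rifampicin accuracy is limited to children with a rifampicin result in both the index and the reference sample.
2. In section 7.e.4, state that a stool or urine Ultra result alone does not make a child confirmed or unconfirmed TB for the composite.
3. From existing CRF fields, identify treated children who are stool- or urine-positive and reference-negative. Report composite sensitivity and specificity with them counted once as TB and once as not TB. Do not rely on exclusion alone.

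The cost is a few sentences, one extra tabulation and a wider reported range for a secondary result. Care, the release of urine results and the 6.a analysis need not change. A CRF field on whether the index result contributed to treatment would narrow the bounds, but it is optional and would help only children still to be enrolled.

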- Using the sterile pipette provided, aspirate the liquefied sample into the pipette until the meniscus is above the minimum mark. Add the mixture into the Xpert MTB/Rif cartridge and insert the cartridge into the GeneXpert instrument and conduct the assay according to the manufacturer's instructions (follow your laboratory Sop for operation of the GeneXpert Instrument).

Interpretation of test results:

- Interpret the results as you normally do with results from sputum samples processed in Xpert Instrument.
- The results are produced by the GeneXpert DX System from measured fluorescent signals and embedded calculation algorithms and will be displayed in the "View Results" window. Lower Ct values represent a higher starting concentration of DNA template; higher Ct values represent a lower concentration of DNA template.
- MTB Detected=> MTB target DNA is detected. The MTB result will be displayed as High, Medium, Low or Very Low depending on the Ct value of the MTB target present in the sample.
- RIF Resistance Detected=> will be displayed if the mutation in the rpoB gene has been detected. This is only displayed in MTB detected results.
- MTB Not Detected=>MTB target DNA is not detected

Quality control testing

Each GeneXpert test cartridge is a self-contained test device with an in-built control for each sample. Normally, no external controls are required. The internal controls enable the system to detect specific failure modes within each for each sample

- Instrument system control: Check status-it checks the optics, temperature of the module and the mechanical integrity of each cartridge. If the system controls fail, an ERROR test result will be reported.
- Probe Check control (PCC): after sample preparation, bead reconstitution and tube filling (prior to thermal cycling), multiple fluorescent readings are taken at different temperatures and compared to default setting. PCC controls for:
 - Missing target specific reagent (TSR) and or enzyme reagent beads which contain all primers, probes and internal control template.
 - Incomplete reagent reconstitution
 - Incomplete reaction tube filling
 - Probe degradation
- If the PCC fails, an ERROR test result will be reported.

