Appendix 12: SOP for Xpert MTB/RIF assay performance

Xpert MTB/RIF assay is based on hemi-nested real time PCR for simultaneous detection of M. tuberculosis (MTB) and rifampicin (RIF) resistance. The target is the *rpoB* gene, critical for detection of mutations associated to rifampicin resistance. Xpert MTB/RIF automates all aspects of real time PCR analysis, with results available in 2 hours.

Sample processing

The test can be performed using fresh sputum samples or decontaminated samples prior culture inoculation.

Procedure with fresh sputum samples:

- Ask the patient to rinse the mouth twice before collecting the sample.
- Collect a minimum of 1.5 ml good quality sputum.
- Follow the procedures outlined below:

Procedure for Xpert MTB/RIF*

Step 1	Step 2	Step 3
 Add the reagent 2:1 (v/v) to the sample and shake 10-20 times. Incubate at room temperature for 15 min.; during incubation repeat once shaking for 10- 20 times.	 With a pipette transfer the diluted sample into a cartridge.	 Insert the cartridge in the machine and start the test.

* Source: National Health Laboratory Services, South Africa.

Procedure for sediment samples:

- Sediments can be prepared according to standard decontamination procedure (NALC-NaOH method) and re-suspend with phosphate buffer.
- Ensure 0.5 ml is available for the test; add 1.5 ml of reagent for 0.5 ml of re-suspended sediment.
- Follow the procedure described in the above figure.

Interpretation of the results:

Proper test performance is ensured by 2 internal controls:

- Sample processing control (SPC) ensures adequate processing and monitors presence of inhibition.
- Probe check control (PCC) verifies that the steps of the tests (rehydration, filling of the cartridge, etc.) take place correctly.

When the test is completed the display can show:

- “MTB detected” expressed by levels (the higher the level, the higher the amount of MTB detected in the sample) or “MTB not detected”;
- RIF results expressed as “detected”, “not detected” or “indeterminate” are available only if MTB is detected.

Other possible results:

- Invalid: MTB invalid and SPC failed due to one of several reasons, such as inhibition;
- Error: MTB no result, SPC no result, PCC failed; fail of system components;
- No result: e.g. tests stopped during processing.

Storage of samples and cartridges:

Samples:

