Appendix 17: CRF Lab

Patient study code:

Respiratory Xpert MTB/RIF Ultra

Date of sample collection: / /

Type of procedure:

- Spontaneous sputum
- Naso-pharyngeal aspirate
- Gastric aspiration

Date of Xpert MTB/RIF performed: / /

Result of Xpert MTB/RIF:

- Negative
- Positive RIF resistance negative
- Positive RIF resistance positive
- Indeterminate

Respiratory Xpert MTB/RIF Ultra (second sample if done)

Date of respiratory sample collection: / /

Type of procedure:

- Spontaneous sputum
- Naso-pharyngeal aspirate
- Gastric aspiration

Date of Xpert MTB/RIF in respiratory sample performed: / /

Result of Xpert MTB/RIF:

- Negative
- Positive RIF resistance negative
- Positive RIF resistance positive
- Indeterminate

Validated extra pulmonary Xpert MTB/RIF Ultra

Date of sample collection: / /

Type of sample:

- Lymph node
- Pus or tissue Specify location:
- Pleural effusion
- CSF
- Ascetic fluid
- Other Specify:

Date of Xpert MTB/RIF in respiratory sample performed: / /

Result of Xpert MTB/RIF:

- Negative
- Positive RIF resistance negative
- Positive RIF resistance positive
- Indeterminate

Validated extra pulmonary Xpert MTB/RIF Ultra

Date of sample collection: / /

Type of sample:

- Lymph node
- Pus or tissue Specify location:

Pleural effusion

CSF

Ascetic fluid

Other

Specify:

Date of Xpert MTB/RIF in respiratory sample performed: / /

Result of Xpert MTB/RIF:

Negative

Positive RIF resistance negative

Positive RIF resistance positive

Indeterminate

Stools Xpert MTB/RIF Ultra

Date of stools collection: / /

Date of Xpert MTB/RIF in stools performed: / /

Result of Xpert MTB/RIF:

Negative

Positive RIF resistance negative

Positive RIF resistance positive

Indeterminate

Stools Xpert MTB/RIF Ultra (second sample if done)

Date of stools collection: / /

Date of Xpert MTB/RIF in stools performed: / /

Result of Xpert MTB/RIF:

Negative

Positive RIF resistance negative

Positive RIF resistance positive

Indeterminate

Urine Xpert MTB/RIF Ultra

Date of urine collection: / /

Date of Xpert MTB/RIF in urine performed:

Result of Xpert MTB/RIF:

Negative

Positive RIF resistance negative

Positive RIF resistance positive

Indeterminate

Urine Xpert MTB/RIF Ultra (second sample if done)

Date of urine collection: / /

Date of Xpert MTB/RIF in urine performed: / /

Result of Xpert MTB/RIF:

Negative

Positive RIF resistance negative

Positive RIF resistance positive

Indeterminate

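### The Xpert Ultra result field has no code for failed runs and does not mark 'indeterminate' as MTB-positive, and section 10 does not say how either enters the accuracy tables

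*Combined protocol and SAP*

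**What the plan says.** Section 8.d.3 (lab exams information) gives the same list of codes for the respiratory, stool and urine tests: "Result of Xpert MTB/RIF Ultra (negative, positive RIF resistance negative, positive RIF resistance positive, indeterminate". The lab CRF in Appendix 17 uses these four codes in all eight result blocks, two each for respiratory, extrapulmonary, stool and urine samples. Two of the codes carry the word positive, for example "Positive RIF resistance positive". The code 'indeterminate' stands alone.

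Appendix 12 describes what the instrument can report. RIF results, including indeterminate, "are available only if MTB is detected". Three further outputs are listed apart from these:

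- The first arises when the sample control does not pass: "Invalid: MTB invalid and SPC failed due to one of several reasons, such as inhibition".
- The second covers a fault in the probe check or the equipment: "Error: MTB no result, SPC no result, PCC failed; fail of system components".
- The third covers a run that did not finish: "No result: e.g. tests stopped during processing".

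The stool SOP (Appendix 10) adds: "If the PCC fails, an ERROR test result will be reported". The urine SOP (Appendix 11) says the same. Both SOPs tell staff to read stool and urine results in the way they read sputum results.

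On repeats, section 8.b.2 provides for a second test after 1 to 2 weeks when the first is negative and symptoms persist. Appendix 17 has blocks for a further sample, for example "Stools Xpert MTB/RIF Ultra (second sample if done". Section 10 names the sensitivity and specificity of stool and urine Xpert as the main outcome. It gives no rule for RIF-indeterminate results or failed runs.

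**The concern.** The list of codes is closed, and it does not match the outputs that the protocol itself describes. An MTB-detected, RIF-indeterminate result belongs on the positive side of the accuracy table, but its code does not say so. A failed run belongs on neither side and has no code at all.

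If failed runs are entered under 'indeterminate', one code holds two kinds of result that need opposite handling, and a later analyst could not separate them from the dataset alone. The same codes serve the stool and urine index tests and the respiratory and extrapulmonary reference tests. The ambiguity can therefore touch both test positivity and the classification of confirmed TB. Without a rule in section 10, the handling could also be chosen after the results are known.

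**Working it through.** **Outputs set against codes**

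| Instrument output (Appendix 12) | Status for MTB | Code on the form |
|---|---|---|
| MTB not detected | negative | negative |
| MTB detected, RIF resistance not detected | positive | positive, RIF resistance negative |
| MTB detected, RIF resistance detected | positive | positive, RIF resistance positive |
| MTB detected, RIF indeterminate | positive | indeterminate (not labelled positive) |
| Invalid, error, no result | none | no code |

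'Negative' is not a proper home for an invalid run. The control rule in Appendices 10 and 11 requires the sample processing control to be positive when the target is negative. A failed run is therefore left blank or goes under 'indeterminate'.

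**The plan's own figures** (section 7.d.4: sensitivity 60%, precision 12%, reference positivity 20%, 2% without stool)

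- Confirmed cases: n = 1.96² × 0.60 × 0.40 / 0.12² = 64.0, as stated.
- Suspected cases: 64 / 0.20 = 320. Final size: 320 / 0.98 = 326.5, rounded up to 327. Both agree with the plan.

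The sample size arithmetic is not in dispute. The 2% allowance is for children who produce no stool; failed runs have none.

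**Effect per child.** This needs no assumed rate. At 60% sensitivity, 0.60 × 64 = 38.4, so take 38 positive stools among 64 confirmed cases: 38/64 = 59.4%.

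- One of the 38 is RIF-indeterminate and is counted negative: 37/64 = 57.8%, a loss of 1.6 points.
- The same child is excluded: 37/63 = 58.7%, a loss of 0.7 points.

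**One child of each kind under the code.** Suppose one of the 38 positives is RIF-indeterminate and one of the other 26 confirmed cases has a failed run. Setting aside only the failed run gives 38/63 = 60.3%. A single rule for the whole code gives:

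- all positive: 39/64 = 60.9%
- all excluded: 37/62 = 59.7%
- all negative: 37/64 = 57.8%

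None of these returns 60.3%. This shows the mechanism; it is not a forecast.

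**Precision cost of setting failed runs aside.** Assumed failure share f among the 64, with half-width 1.96 × √(0.24/n):

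- f = 0: n = 64, half-width 12.0 points
- f = 2%: n = 64 × 0.98 = 62.7, half-width 12.1 points
- f = 5%: n = 64 × 0.95 = 60.8, half-width 12.3 points

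**The case against.** The strongest reply is that the documents give 'indeterminate' only one meaning. Appendix 12 ties it to a RIF result when MTB is detected, and the stool and urine SOPs send the reader to the sputum interpretation. A site that follows them would not use the code for a failed run; it might leave the field blank, which is missing data and not misclassification. This stands as far as it goes: the documents do not show that sites pool the two. But it supplies no code for a failed run, and it does not put RIF-indeterminate results on the positive side of the table.

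Second, the reference test has a cross-check. The clinical CRF (Appendix 4) records the final diagnosis as confirmed, suspected or unlikely TB. This is a partial check, because section 7.e.4 also allows confirmation by culture, or by TB LAM in HIV-infected patients. No comparable item exists for stool or urine.

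Third, some of the material is not visible. A repeat rule for failed runs may sit in the laboratory SOP to which Appendices 10 and 11 refer. The database may also differ from the form shown: section 8.b.2 says TB LAM results go on the lab CRF, yet Appendix 17 has no LAM field. Section 8.d.3 gives the same four codes independently of that form.

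Three stronger readings are tempting but unsupported:

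- A reader might infer that a trace rule is missing. Appendix 18 is devoted to trace results and its body is not shown, and the background section cites guidance to treat trace in children as positive. No gap can be claimed.
- A reader might take the section 10 sentence comparing Xpert-positive with Xpert-negative patients as proof that the accuracy tables ignore failed runs. It concerns patient characteristics. The finding is only that no rule is stated.
- A reader might attach a definite bias to the main result, for example by assuming that a tenth of positive stools fall under the code. No document supports any such share.

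**Conclusion.** The point holds as a defect in the data field and a missing analysis rule. Invalid, error and no-result runs cannot be recorded as what they are. RIF-indeterminate results, which are MTB-positive under Appendix 12, are not labelled so. The visible text does not say how either enters the tables for the main outcome. Clear negatives, and positives with a RIF call, are not affected.

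The size is unknown because the documents give no rate of RIF-indeterminate results or failed runs. Each MTB-positive stool counted as negative would cost 1.6 points of sensitivity on the planned 64 confirmed cases; whether this happens to any child cannot be told from the documents. That failed runs end up under 'indeterminate' is a possibility that the form leaves open, not a documented practice. The point is worth correcting before analysis because a pooled code cannot be separated later from the dataset alone.

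**What to change.** In section 8.d.3 and Appendix 17, replace the single field with two:

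- MTB: not detected / detected, with the reported level including trace / invalid, error or no result.
- RIF: resistance not detected / resistance detected / indeterminate / not applicable.

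In section 10, state that:

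- any MTB detected, including RIF indeterminate, is test-positive in the accuracy tables for index and reference tests, with trace handled as Appendix 18 sets out;
- failed runs count as neither positive nor negative and are reported by sample type;
- a valid repeat does or does not replace a failed run, citing the laboratory SOP if the rule is there.

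For tests already done, recode from instrument or laboratory records where these were kept, and report how many results could not be recoded.

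The cost is a small change to the CRF and database, one paragraph in section 10, and slightly fewer evaluable results. No new patients are needed. The Summary gives a timeframe of January 2019 to July 2021, and section 8.b.2 refers to November 2021, so much of the testing may be complete. The gain for past tests then depends on records that the documents do not mention; the section 10 rule remains useful if it is set before analysis.
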